8.3. Demographic and Baseline Characteristics

All baseline and demographic data recorded at screening and prior to dosing will be listed.

Subject demographic and baseline characteristics will include age at enrollment, age at AVR-RD-02 infusion, gender, race, ethnicity, height, body weight, BMI, GCase enzyme in peripheral blood, GCase enzyme in DBS, GCase enzyme in plasma, Lyso-Gb1 concentration in plasma, and Chitotriosidase enzyme in plasma.

Data listings will also be provided for:

- Diagnosis information, including age at time of diagnosis and age at onset of symptoms
- Historical mutation analysis
- Transmittable disease testing
- Prior ERT, SRT, and other prior treatments

8.4. Medical History and Medical Conditions Present at Entry

All medical history conditions, concomitant diseases and surgical procedures will be classified by system organ class (SOC) and preferred term (PT) using MedDRA^{*} v23.0. The version will be labelled in the applicable outputs.

Past and current medical conditions will be listed, including whether the subject has experienced any past concomitant diseases or surgeries, start date, end date or whether it is ongoing, the disease or symptom, the SOC and PT, the maximum CTCAE Grade, and whether it resulted in hospitalization.

8.5. Extent of Exposure

AVR-RD-02 infusion drug product characteristics will be obtained from the Certificates of Analysis (CoA).

8.6. Treatment Compliance

All auxiliary medication administration data (G-CSF, plerixafor, busulfan, and anti-convulsant) and AVR-RD-02 infusion will be listed. Apheresis data (e.g., total cell count, CD34+ cell count) will also be listed.

The listing of busulfan will include the dose administered each day, percentage dose increased/decreased vs. the previous dose, percentage difference between expected and actual dose, the start and end times, total dose (mg), body surface area (m²) and total dose/BSA (mg/m²), AUC and Total AUC.

The listing of AVR-RD-02 infusion will include start date and time of infusion, end date and time of infusion, subject weight (kg), total volume infused (mL) and date of initial hospital discharge. If more than one batch of gene therapy was manufactured and administered to the subject, then the sum will also be presented for total volume infused (mL).

A listing will include the dates and derived study day of:

- G-CSF for Mobilization
 - Excludes any G-CSF injections administered after treatment with AVR-RD-02 for hematological reconstitution due to ANC < 0.5 (10⁹/L), which will be listed separately
- Plerixafor
- Apheresis
- Anti-convulsant medication given for prophylaxis ahead of busulfan
- Conditioning with busulfan
- AVR-RD-02 infusion

Since all the above-mentioned administrations will be done at the investigational site, treatment compliance will not be determined for this study.

8.7. Prior and Concomitant Medications

The end dates of medications will be used to assign medications into different categories:

- Prior medication: Prior medications are defined as any medication where the use was stopped prior to the first administration of G-CSF for Mobilization.
- Concomitant medication: Concomitant medications are defined as any medication (other than the auxiliary medications and AVR-RD-02) that was used at least once after the first administration of G-CSF for Mobilization. Medications that were stopped on the same date as G-CSF will be defined as concomitant medications. The answer to the question "Ongoing?" as recorded on the eCRF pages will also be taken into consideration to determine if a medication is classed as concomitant.

Table 5 below shows the algorithm for Prior/Concomitant Medications. For the purposes of the below algorithm, note that if the start date is partial then the start date should be temporarily imputed as the earliest possible date (i.e., first day of month if day unknown or 1st January if day and month are unknown) and if the end date is partial then the end date should be temporarily imputed as the latest possible date (i.e., last day of month if day unknown or 31st December if day and month are unknown):

Start date	End date	Action
Known	Known, Partial or	If end date < start date of mobilization with G-CSF, then not Concomitant
	Missing	Otherwise, if end date \geq mobilization with G-CSF start date, then Concomitant

Table 5: Algorithm for assignment of timing for medication use

Start date	End date	Action
Partial, but known components show that it cannot be on or after mobilization with G-CSF start date	Known, Partial or Missing	Not Concomitant
Partial, could be on or after mobilization with G-CSF start date OR Missing	Known	If end date < mobilization with G-CSF start date, then not Concomitant If end date ≥ mobilization with G-CSF start date, then Concomitant
	Partial	Temporarily impute end date as latest possible date (i.e., last day of month if day unknown or 31 st December if day and month are unknown), then: If imputed end date < mobilization with G-CSF start date, then not Concomitant If imputed end date ≥ mobilization with G-CSF start date, then Concomitant
	Missing	Assumed Concomitant

The start dates and end dates of prior and concomitant medications will be used to further split prior and concomitant medications into the following periods:

- Pre-Mobilization: ended before first dosing of G-CSF
- Auxiliary Medications:
 - Mobilization:
 - G-CSF: started on or after first dosing of G-CSF for Mobilization and before start of apheresis
 - For any subject who received Mobilization twice, the study period between the start of the second Mobilization until the start of the second apheresis will be captured as Mobilization #2
 - o Apheresis:
 - o started on or after start of apheresis until the end of the last apheresis

- For any subject who received Apheresis twice, the study period between the start of the second apheresis until the end of the second apheresis will be captured as Apheresis #2
- Post-Apheresis: started after the end of the last apheresis and before first dosing of anti-convulsant medication given for prophylaxis ahead of busulfan
 - For any subject who received Mobilization twice, the study period between the end of the first apheresis and the start of Mobilization #2 will be captured as Post-Apheresis
 - The study period between the end of the second apheresis and the first dosing of anti-convulsant medication given for prophylaxis ahead of busulfan will be captured as Post-Apheresis #2
 - For any subject who received Mobilization but did not proceed to receive conditioning or AVR-RD-02, the study period after the end of Apheresis will be captured as Post-Apheresis
- Conditioning: started on or after first dosing of anti-convulsant medication given for prophylaxis ahead of busulfan and before date of AVR-RD-02 infusion
- AVR-RD-02 Infusion: started on or after the start of infusion of AVR-RD-02
- Post-AVR-RD-02 Infusion Follow-Up: started after the end of AVR-RD-02 infusion

Note since only dates are captured for medications, and not times, that the start/end dates will be used to assign medications to a period, e.g., a medication starting on Study Day 1 will be assigned to the AVR-RD-02 infusion period because it is not known if the medication started before or after the start time of the AVR-RD-02 infusion on Day 1.

Medications will be classified as a prior medication and/or a concomitant medication. The prior and concomitant medications are exclusive with each other. The same concomitant medication, however, could appear in multiple periods of Mobilization, Apheresis, Post-Apheresis, Conditioning, AVR-RD-02 Infusion, and Post-AVR-RD-02 Infusion Follow-Up, if it was used in two or more of those periods.

Prior and concomitant medications do not include G-CSF, plerixafor, busulfan, and anticonvulsant medication administration for seizure prophylaxis. However, any G-CSF administered due to ANC < 0.5 ($10^{9}/L$), beginning Day 30 after treatment with AVR-RD-02, will be listed separately.

Similarly, any platelet transfusions will be listed separately.

Prior and concomitant medications will be coded by WHODrug Global B3 March 2018.

Prior medication and concomitant medications will be listed. The period and within period study day for medication start and stop and all periods where the medication has been used will be provided. For concomitant medications, medication name, product name, start dates and end dates, dose, dose unit, frequency, route, and indication (including details of any associated MH or AE) will be presented. Concomitant medications which started prior to a subject's first auxiliary medication will be flagged.

The auxiliary medications (G-CSF, plerixafor, busulfan, or anti-convulsant) will be listed separately (see Section 8.5).

Listings will be sorted by subject identification number and start date. If the start date is completely missing, then these events will be presented first. If the onset date is missing a month or a day then partial dates for medications will be imputed as per Table 5 to allow medications to be sorted appropriately. Imputed dates will not be listed.

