Figure 1: Clinical Study Design for AVRO-RD-02-201
Switch-stable Arm

Abbreviation: DMC = Data Monitoring Committee.

Five study periods (Screening, Baseline, Pre-gene Therapy Infusion, Gene Therapy Infusion, and Post-gene Therapy Infusion Follow-up) comprise the study. During the Screening Period (up to 60 days), written informed consent will be obtained and the subject will complete other Screening procedures to confirm study eligibility. Once study eligibility is confirmed, subjects will enter the Baseline Period (up to 7 days) during which time assessments will be performed to establish pre-gene therapy infusion baseline. Once Baseline assessments are complete, the subject will enter the Pre-gene Therapy Infusion Period (approximately 8 weeks to 10 weeks [in some instances, the Pre-gene Therapy Infusion Period may be extended beyond 10 weeks due to subject and/or site availability to initiate conditioning]) during which time mobilization, apheresis, AVR-RD-02 investigational product preparation and testing for release, conditioning regimen administration, and conditioning washout period will take place. Enzyme replacement therapy must be discontinued at least 2 weeks before the scheduled gene therapy infusion day. Following completion of the Pre-gene Therapy Infusion Period, the subject will enter the Gene Therapy Infusion Period (1 day) during which AVR-RD-02 gene therapy infusion will take place. After AVR-RD-02 gene therapy infusion, the subject will enter the Post-gene Therapy Infusion Follow-up Period (approximately 52 weeks) during which time periodic safety and efficacy assessments will be performed to assess measures of safety, engraftment, and clinical response post-gene therapy infusion. Post-gene therapy infusion follow-up will occur at the following time points: Week 1 (Days 1 through 7), Week 2 (Days 10 and 14), Week 5 (Day 30), Week 9 (Day 60), Week 13 (Day 90), Week 18 (Day 120), Week 22 (Day 150), Week 26 (Day 180), Week 39 (Day 270), and Week 52 (Day 365). Subjects that withdraw any time after gene therapy infusion or complete this study have the opportunity to participate in the long-term follow-up study. During the post-gene therapy infusion period, subjects will not receive ERT unless prespecified laboratory and clinical criteria, which suggest the need for ERT initiation, are met.

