The Screening through Pre-gene Therapy Infusion Period could be as long as 21 weeks. To avoid any significant interruption of enzyme replacement for switch-stable subjects, ERT will be continued up to 2 weeks before the scheduled gene therapy infusion day. This 2-week timeframe should serve as an adequate washout period for the replacement enzyme before gene therapy infusion is initiated. This timeframe is based on the pharmacokinetics (PK) and clearance of commercially available ERTs and the corresponding dosing frequency recommendations (see the package inserts for imiglucerase, velaglucerase alfa, and taliglucerase alfa).

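### SAP Table 5 labels a drug with a partial, clearly pre-mobilization start date Not Concomitant whatever its end date, against section 8.7's own definition

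*SAP*

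**What the plan says.** SAP section 8.7 opens with the basis of classification: "The end dates of medications will be used to assign medications into different categories". It then gives two definitions.

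- Prior: "Prior medications are defined as any medication where the use was stopped prior to the first administration of G-CSF for Mobilization".
- Concomitant: any medication, other than the auxiliary medications and AVR-RD-02, "that was used at least once after the first administration of G-CSF for Mobilization". A drug stopped on the day of G-CSF counts as concomitant.

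The answer to the eCRF question on whether the drug is ongoing, "as recorded on the eCRF pages will also be taken into consideration to determine if a medication is classed as concomitant".

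SAP Table 5 turns this into rules. With a complete start date, the end date decides: "If end date < start date of mobilization with G-CSF, then not Concomitant", and otherwise Concomitant. With a start date that is missing, or partial but possibly on or after G-CSF, the end date again decides, and a missing end date is assumed Concomitant. The row between these two covers a start date that is "Partial, but known components show that it cannot be on or after mobilization with G-CSF start date". It accepts any kind of end date and has one action, Not Concomitant.

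On ERT, Protocol section 6.2.1 says that for switch-stable subjects "ERT will be continued up to 2 weeks before the scheduled gene therapy infusion day". SAP section 5.1 confirms that only switch-stable subjects were enrolled.

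**The concern.** The middle row decides on the start date alone, although the section says that end dates decide. The likely source is SAP Table 3, the treatment-emergence algorithm for adverse events, which has a row of the same form. It is right there, because treatment emergence depends on onset. Medication status depends on use, and a drug begun years before mobilization may still be in use after it.

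At stake is the accuracy of the prior and concomitant medication listings. Section 8.7 also calls for a flag on concomitant medications that began before the first auxiliary medication. Every drug in this row began before G-CSF, so each one that was still in use afterwards should carry that flag. A drug labelled Not Concomitant cannot.

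**Working it through.** The plan gives no figure to reproduce. The check applies the definition and SAP Table 5, as written, to one course of ERT and varies only how complete the start date is.

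**Inputs**

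- Length of the period that begins with mobilization: "Pre-gene Therapy Infusion Period (approximately 8 weeks to 10 weeks" (Protocol section 6.1).
- ERT stop: 2 weeks before infusion (Protocol section 6.2.1).
- Day 0: first G-CSF dose.

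**When ERT ends**

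Days from first G-CSF to last ERT = 7 × (weeks in period) − 14.

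- 8 weeks: 56 − 14 = 42 days.
- 10 weeks: 70 − 14 = 56 days.

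Both fall after first G-CSF, so the text definition makes ERT concomitant.

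**What SAP Table 5 returns**

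| Start date | End 42 or 56 days after G-CSF | End before G-CSF | End date missing |
|---|---|---|---|
| Complete | Concomitant | Not Concomitant | no action given |
| Partial, certainly before G-CSF | **Not Concomitant** | Not Concomitant | **Not Concomitant** |
| Partial, possibly on or after G-CSF | Concomitant | Not Concomitant | Concomitant (assumed) |
| Missing | Concomitant | Not Concomitant | Concomitant (assumed) |

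Three things follow.

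1. For a drug stopped after G-CSF, only the second line contradicts the definition. A start date known to the month or year gives the wrong label, while no start date at all gives the right one.
2. The second line is right only when the end date is before G-CSF, and the row does not ask for that.
3. The first line admits a missing end date but assigns it no action.

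The 42 to 56 days are indicative. Protocol section 6.1 lets the period run beyond 10 weeks and requires ERT to stop at least 2 weeks before infusion, so a subject may stop earlier. A footnote to the second schedule of assessments (Protocol section 15.2) places 8 to 10 weeks between apheresis and conditioning alone. The conclusion does not need the exact number: any stop on or after first G-CSF is enough.

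**With the end-date rule in the second line**, ERT stopped at 42 or 56 days is Concomitant for all four kinds of start date, in agreement with the text.

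**The case against.** **The ongoing question is a safeguard.** A drug marked ongoing could be classed as concomitant despite the table. This stands in part. The answer is only one consideration, with no stated precedence over Table 5. It also does not help a drug with a recorded stop after G-CSF, such as ERT ended before infusion.

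**The note above Table 5 says to impute a partial start date to the earliest possible date.** If that were done first, every partial start would become complete and the first row would apply. But the table has separate rows for partial start dates, with their own actions, and this reading would leave them unused. At best it shows that two programmers could get different answers.

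**The consequences are small.** This stands. Section 8.7 specifies listings, SAP section 5.1 shows partial dates as captured, and the SAP was written for an abbreviated report of a study stopped early. Prior ERT has its own listing (SAP section 8.3), and the rationale, frequency and doses of ERT are listed under SAP section 9.3.2.

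A reader might infer more than the documents support:

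- *That period of use would be wrong.* Section 8.7 derives periods in a separate step from start and end dates. The Pre-Mobilization period requires the drug to have ended before G-CSF, so ERT ended later does not enter it.
- *That the drug disappears from both categories.* Section 8.7 classes each medication as prior or concomitant and calls the two exclusive, so a drug denied one label most naturally receives the other. That label breaks the definition of prior, but the record is still listed.
- *That efficacy results are affected.* SAP section 9 never uses the label, strata, covariates and subgroups are not applicable (SAP sections 7.2 and 7.3), and no tests or models are planned (SAP section 2.3).

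**Conclusion.** The row is wrong as written: it contradicts the definition in the same section and the results that SAP Table 5 gives for the same drug in its other rows. The severity is minor. The effect is a wrong prior or concomitant label, and a missed flag, for long-term drugs with a partial start date before G-CSF and use continuing after it.

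ERT is the most relevant example, since switch-stable subjects need at least 24 consecutive months of it before Screening. That its start date is often partial is an assumption about the data. All enrolled subjects were switch-stable, so a reader might infer that every subject is affected. The documents do not say how many start dates are partial, so the number could lie anywhere from none to all.

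**What to change.** In SAP Table 5:

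1. Replace the action for a partial start date certainly before G-CSF with the end-date rule. Impute a partial end date to the latest possible date, as the section already provides. An end date before first G-CSF gives not Concomitant, and one on or after it gives Concomitant. A missing end date, or a drug marked ongoing, is assumed Concomitant.
2. Add the same action for a missing end date to the complete-start row, which has none.

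The cost is two table cells and the matching lines of code. No new data are needed. SAP section 1 allows amendments before database lock; after lock, the change would be documented and justified in the study report.

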Busulfan crosses the blood-brain barrier and can cause neurotoxicity, including seizures, when administered at higher doses. Therefore, anticonvulsant medication is routinely prescribed for patients undergoing myeloablative therapy with busulfan in preparation for bone marrow transplant (BMT) or hematopoietic cell transplant (HCT). Consistent with this practice, anticonvulsant prophylaxis will be administered concurrent with busulfan administration for conditioning in this study. Levetiracetam will be administered in this study as described in Section 8.1.1.3. The dosing regimen selected for levetiracetam has been shown in literature to be effective at preventing seizures in adults receiving conditioning with busulfan in preparation for HSCT, and to have an acceptable safety profile when administered in combination with busulfan (Akiyama 2018). For subjects with contraindications to levetiracetam, an alternative anti-

convulsant medication (eg, benzodiazepines or valproic acid) may be used before and after busulfan treatment (Busulfan PI).

Busulfan treatment at the approved dose and schedule produces profound, transient myelosuppression in all patients. Hematologic changes have been observed in subjects receiving myeloablative busulfan conditioning regimens used in other autologous LV-mediated gene therapy studies for TDT, sickle cell disease (SCD), metachromatic leukodystrophy (MLD), leukocytes adhesion deficiency-1, and X-linked chronic granulomatous disease (Fumagalli 2022; Sessa 2016; Thompson 2018; Tisdale 2018; Kohn 2020; see also the Investigator's Brochure for AVR-RD-02). Similar outcomes were achieved by Mamcarz et al in LV-mediated gene therapy for X-linked severe combined immunodeficiency (SCID-X1) patients, albeit targeted busulfan was indicated at low dose (Mamcarz 2019).

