 - a. For male subjects and for male spouses/partners of female subjects, condoms are an acceptable method of barrier contraception.
 - b. For female subjects and for female spouses/partners of male subjects, acceptable methods of barrier contraception include diaphragm, cervical cap, or contraceptive sponge.

- 7. Male and female subjects must agree to refrain from donating sperm and eggs, respectively, after undergoing conditioning.
- 8. Subject must be willing to refrain from donating blood, organs, tissues, or cells for gene therapy infusion any time after AVR-RD-02 treatment.
- 9. Subject must be willing to receive blood or blood products transfusion to manage AEs.

Additional Inclusion Criteria for Switch-stable Subjects:

In addition to inclusion criteria 1 through 9, switch-stable subjects must meet all of the following inclusion criteria for participation in this study:

- 10. Subject has undergone a stable dose (within 75% to 125% of the prescribed dose) of ERT ≥ 15 U/kg and ≤ 60 U/kg every other week (or equivalent; ie, any combination of infusions resulting in a total monthly ERT dose of ≥ 30 U/kg and ≤ 120 U/kg) for ≥ 24 consecutive months with no significant interruptions, in the opinion of the Investigator, in dosing over the last 6 months prior to Screening.
- 11. Subject has normal or near-normal hematologic values at Screening defined as one or more of the following:
 - a. Hemoglobin concentration $\geq 10g/dL$
 - b. Platelet count $\geq 80 \times 109/L$
- 12. Subject has stable Gaucher disease during the 6 months immediately preceding Screening defined by:
 - a. Stable hemoglobin concentration (ie, within a range of \pm 2 g/dL of the Screening value) based on documented historical clinical laboratory results

and

Stable platelet count (within \pm 20% of the Screening value) based on documented historical clinical laboratory results

13. Subject has not received SRT for Gaucher disease during the 12 months immediately preceding Screening.

Additional Inclusion Criteria for Treatment-naïve Subjects:

In addition to inclusion criteria 1 through 9, treatment-naïve subjects must meet the following inclusion criteria for participation in this study:

- 14. Subject has never received either ERT or SRT for Gaucher disease or has not received either ERT or SRT for Gaucher disease within 12 months of Screening.

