9.1.2. Hemoglobin Concentration

Observed values and absolute change from baseline in hemoglobin values will be listed. Any decreases from baseline of >2 (g/dL) will be flagged on the listing.

Hemoglobin values relative to baseline, derived as post-baseline value/baseline value, will also be listed, and any values <0.8, indicating hemoglobin concentrations < 80% of the baseline value, will be flagged on the listing.

Figures displaying individual values over time, with study week on the x-axis, along with arithmetic or geometric means, will also be provided. A horizontal reference line will be added to indicate a CFB of -2 (g/dL).

A figure displaying individual values relative to baseline over time, with study week on the x-axis, along with arithmetic or geometric means, will also be provided. A horizontal reference line will be added at 0.8 to indicate any hemoglobin concentration < 80% of the baseline value.

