9.1.3. Platelet Count

Platelet counts will be listed. Any values $<35 (10^{9}/L)$ will be flagged on the listing.

Platelet counts relative to baseline, derived as post-baseline value/baseline value, will also be listed, and any values <0.8, indicating platelet count <80% of the baseline value, will be flagged on the listing.

Figures displaying individual values over time, with study week on the x-axis, along with arithmetic or geometric means, will also be provided. A horizontal reference line will be added at $35 (10^9/L)$.

A figure displaying individual values relative to baseline over time, with study week on the xaxis, along with arithmetic or geometric means, will also be provided. A horizontal reference line will be added at 0.8 to indicate any platelet count < 80% of the baseline value.

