10.1.1. Achievement of Hematological Engraftment

The occurrence of hematological reconstitution is defined as the first day of absolute neutrophil count (ANC) $\ge 0.5 (10^9/L)$ and of platelets $\ge 20 (10^9/L)$ (in the absence of platelet transfusions), i.e. time (days) from date of AVR-RD-02 infusion to the first date of the three consecutive values.

For the Infused Population, panel plots of individual subjects will be presented for ANC $(10^9/L)$ between study day -50 and study day 100, with study day on the x-axis. Vertical reference lines will be included at study day 1 (solid, black), 35 (dashed, red), 42 (solid, red) and 49 (dashed, red) and to represent the study day the subjects received their AVR-RD-02 infusion and their first and last doses of busulfan. A horizontal reference line will be included at 0.5 ($10^9/L$). On the x-axis, red arrows will indicate the study days that G-CSF was administered.

For the Infused Population, panel plots of individual subjects will be presented for platelet counts $(10^9/L)$ between study day -50 and study day 100, with study day on the x-axis. Vertical reference lines will be included at study day 1 (solid, black), 35 (dashed, red), 42 (solid, red) and

49 (dashed, red) and to represent the study day the subjects received their AVR-RD-02 infusion and their first and last doses of busulfan. Horizontal reference lines will be included at 20 and 35 $(10^9/L)$. On the x-axis, red arrows will indicate the study days that any platelet transfusions were administered.

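### The SAP does not tie red-cell transfusions to the primary hemoglobin outputs, nor its own platelet-transfusion handling to the primary platelet outputs

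*SAP*

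**What the plan says.** Transfusion is foreseen. Protocol 6.2.2.2 states: "Busulfan treatment at the approved dose and schedule produces profound, transient myelosuppression in all patients". Inclusion criterion 9 (Protocol 7.1) reads: "Subject must be willing to receive blood or blood products transfusion to manage AEs".

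The SAP deals with transfusion in two places, both for platelets only:

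- Section 8.7 gives platelet transfusions their own listing: "Similarly, any platelet transfusions will be listed separately".
- Section 10.1.1 (Achievement of Hematological Engraftment) counts platelet recovery only "in the absence of platelet transfusions". For the individual platelet panels, which run from study day -50 to 100, it adds: "On the x-axis, red arrows will indicate the study days that any platelet transfusions were administered".

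The primary efficacy sections do not refer to transfusion:

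- Section 9.1.2: "Hemoglobin values relative to baseline, derived as post-baseline value/baseline value, will also be listed". Ratios below 0.8 and falls of more than 2 g/dL are flagged. Individual values are plotted with a mean line.
- Section 9.1.3: "Platelet counts relative to baseline, derived as post-baseline value/baseline value, will also be listed". Ratios below 0.8 and counts below 35 (10^9/L) are flagged, again with plots and a mean line.

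No general rule fills the gap. Section 7.5.3 takes the measurement nearest the planned date, and 5.7.11 keeps outliers in every output.

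**The concern.** The SAP accepts that a platelet count supported by transfusion is not recovery, but applies this only to a safety definition and a plot that ends at study day 100. The same counts enter the primary efficacy displays unmarked. For hemoglobin there is no handling at all, although the documents protect that endpoint from other influences: red-cell growth factors are excluded through Week 52 (Protocol 7.2, criterion 25), and erythropoietin use is an important deviation (SAP 8.2).

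SAP 5.1 says that only switch-stable subjects were enrolled. Their baseline was established on ERT, so a count that stays level is the favourable pattern, and an unmarked transfusion pushes the display that way. With no tests or models planned (SAP 2.3), these listings and figures are the evidence.

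**Working it through.** The documents give no figure on this point to reproduce. The check applies the SAP's own flag rules. Baselines, falls and rises below are assumptions for illustration.

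**1. Hemoglobin.** Let b be baseline, d the true fall and r the rise still present from a transfusion when the sample is drawn. The observed fall is d - r.

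- Flag A (SAP 9.1.2) fires if d - r > 2 g/dL.
- Flag B (SAP 9.1.2) fires if (b - d + r)/b < 0.8, that is, if d - r > 0.2b.

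For b of 10 g/dL or more, 0.2b is at least 2, so B never fires without A. Both are silent when d - r is 2 or less, and the hidden band is 2 < d ≤ 2 + r. For b = 9, 0.2b = 1.8, so B fires first and the band is 1.8 < d ≤ 1.8 + r.

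Observed fall (g/dL) and result for baselines of 10, 12 and 14:

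| True fall d | r = 0.5 | r = 1.0 | r = 2.0 |
|---|---|---|---|
| 2.1 | 1.6, no flag | 1.1, no flag | 0.1, no flag |
| 2.5 | 2.0, no flag | 1.5, no flag | 0.5, no flag |
| 3.0 | 2.5, flagged | 2.0, no flag | 1.0, no flag |
| 5.0 | 4.5, flagged | 4.0, flagged | 3.0, flagged |

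Without transfusion, every row triggers flag A. The masking is confined to the band. With b = 12, d = 5 and r = 2, the observed value is 12 - 5 + 2 = 9, a fall of 3 and a ratio of 9/12 = 0.75, so both flags fire.

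**2. Platelets.** True counts of 20, 30 and 34, rises of 5, 15 and 30, and baselines of 80, 120 and 200 (all 10^9/L) give 27 combinations.

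- The below-35 flag is lost in 24. It survives only for 20 + 5 = 25, at each of the three baselines.
- The below-0.8 flag survives in 26. It is lost only for (34 + 30)/80 = 0.80, which is not below 0.8.

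**3. Mean line.** One subject with a residual rise r shifts an arithmetic mean by r/n. With r = 1 g/dL the shift is 1/3 = 0.33 g/dL at n = 3, 1/4 = 0.25 at n = 4, 1/8 = 0.125 at n = 8, and 1/16 = 0.06 at n = 16. The plan was for approximately 8 to 16 subjects. The study stopped early and the documents give no number infused, so 3 and 4 are assumed.

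**4. Visits.** Protocol Table 6 schedules central hemoglobin and platelet samples on Days 30, 60, 90, 180, 270 and 365. The primary endpoints use Weeks 13, 26, 39 and 52 (Days 90 to 365). Days 30 and 60, closest to the myelosuppression, are plotted but are not endpoint visits. The platelet arrows reach study day 100, which covers the Week 13 target but not Weeks 26, 39 or 52.

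**The case against.** A reader might infer that red-cell transfusions are listed nowhere. The documents do not support that. Concomitant medications and therapies are recorded from consent to Week 52 (Protocol Tables 4 to 6, footnotes). SAP 8.7 states "Prior medication and concomitant medications will be listed", with dates, dose and indication. The AE listing shows treatment given (10.1.1.8), and section 7 promises listings of everything in the database. The eCRF is not available, so neither presence nor absence can be shown.

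A reader might also infer that platelet failure could pass unseen. That goes too far. The ratio flag nearly always survives, the safety listing flags counts below 35 and below 20 (SAP 10.1.3), Grade 3 or higher platelet counts are AEs whatever their clinical significance (Protocol 9.2.1), and transfusions are listed and marked to study day 100.

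Nor do the documents show that the primary endpoints are biased in fact. They give no transfusion frequency, and criterion 9 requires willingness, not use. A low hemoglobin measured before transfusion would still be listed with change from baseline and low/high and clinical-significance flags (10.1.3). ERT decisions do not run on the SAP flags: for switch-stable subjects, Protocol 7.4.6.2 requires two or more parameters over two consecutive visits and investigator judgment.

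All of this limits the point without removing it. A general listing does not tell the reader of a hemoglobin figure which points followed a transfusion, and the hemoglobin safety listing has no threshold flag like the platelet one.

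**Conclusion.** The point holds as a gap in linkage and display, mainly for hemoglobin. Red-cell transfusions are not named, not listed separately and not connected to the outputs in 9.1.2. Platelet transfusions are listed, but the SAP's handling of them does not reach 9.1.3.

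For hemoglobin, a true fall modestly above 2 g/dL can go unflagged at the visit, and the value enters the mean line as a maintained count. The width of that band equals the residual rise, which is an assumption (0.5 to 2.0 g/dL was tried). For platelets, the below-35 flag can be lost but the ratio flag usually remains. The endpoint visits are touched only if transfusion support is late or prolonged, which is when a reader most needs to see it. The actual effect is unknown. The error favours the product and correction is cheap, so the change should be made, but no formal inference depends on it.

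**What to change.** Amend the SAP before database lock:

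1. In 8.7, list red-cell transfusions separately, with dates and units, as is done for platelet transfusions.
2. In 9.1.2 and 9.1.3, mark on the listings and figures, through Week 52, each hemoglobin value that follows a red-cell transfusion and each platelet value that follows a platelet transfusion, within an interval fixed before lock.
3. If any value is marked, also show the mean line without the marked values. If none is marked, state that and add nothing.

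No value is removed from the listings, so the rule of including all observations is kept. The cost is one derived flag and slightly busier figures. It relies on therapies already due to be recorded to Week 52. The sponsor should confirm that the eCRF identifies red-cell transfusions with dates and units.
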